- 3) To qualitatively study the in-depth characteristics of study subjects who a) documented many overdosed reversals/"saved" many community members, b) documented one overdose reversal/"saved" one community member, and c) did not document any overdose reversals.
- 4) Study the 2 mg Evzio autoinjector product to prospectively analyze the difference in doses (2 mg vs. 0.4 mg) needed to reverse an overdose. The goal will be to recruit 100 patients in one year and document between 20-30 overdose reversals in the community.

Note: Between April 4th 2016 and April 4th 2017, 383 study subjects were enrolled and there were 93 reported overdose reversals. We are currently enrolling new patients at the rate of 6-10 new patients per month.

2. Background

a. The use of naloxone auto-injectors to block the pharmacological effects of opioid medications may have a positive impact on the overdose deaths from prescription opiates if utilized in a manner similar to other emergency devices. Several formulations are available including intravenous, intramuscular, and subcutaneous injections, all of which are commonly used administration routes. Adverse events due to opioid overdose can occur in many situations, and risk of death increases if treatment is not administered immediately. Because of respiratory depression, there is not enough time for patient transport to the emergency room before treatment is initiated. The risk of death, and/or cerebral hypoxia/anoxia increases substantially. A formulation of naloxone that is easy to administer under any condition could be utilized as a "rescue kit" in the same conceptual manner of "Universal Precautions" as a glucagon injection is used for a person that uses insulin to control blood sugar in an emergency.

According to the National Survey on Drug Use and Health, between 55% of patients dying of an unintentional opioid overdose obtain their medication from a friend or relative.¹ 17.3% of patients dying of an unintentional opioid overdose obtain their medication directly from one doctor. Additionally, unintentional opioid overdoses remain the third leading cause of childhood poisonings at 7.9% of all childhood poisonings (after cosmetics and cleaning products).²

b. Drug Prescription Overdose Death in the United States and New Mexico

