Since April 2016, we have enrolled 358 patients at ASAP in our prospective nonrandomized clinical trial using the Evzio autoinjector. We have documented 82 overdose reversals thus far. Only one of the reported overdose reversals was from the study patients at ASAP, while the other 81 overdose reversals were from community members received naloxone from the study patients. For every 100 patients enrolled in the study, approximately 23 overdose reversals have been reported. We have submitted a peer-reviewed article about this data, and are now waiting to hear back regarding acceptance of the submission.

3. Study Design

- 3.1. The previous study at ASAP is a prospective observational study using the naloxone 0.4 mg auto-injector which took place April 4th, 2016 through April 30th, 2017.
- 3.2. Evaluation of patients enrolled include: # overdoses reversed, # naloxone doses needed, urine toxicology, history of overdoses witnessed, history of being reversed by naloxone, demographic information, medical history, etc.
- 3.3. For this current study, we propose the following new additional studies:
 - A biostatistical logistic regression analysis to study the characteristics of the study subjects who performed the overdose reversals (vs. the study subjects who did not).

8 | [Type text]

- A qualitative study to examine in-depth the characteristics of study subjects who a) documented many overdosed reversals/"saved" many community members, b) documented one overdose reversal/"saved" one community member, and c) did not document any overdose reversals
- Study the 2 mg Evzio autoinjector product to prospectively analyze the difference in doses (2 mg vs. 0.4 mg) needed to reverse an overdose. The goal will be to recruit 100 patients in one year and document between 20-30 overdose reversals in the community.

4. Inclusion and Exclusion Criteria

Inclusion Criteria

- A. All patients treated with naltrexone, methadone or buprenorphine as medication assisted treatment at the UNM Addiction and Substance Abuse Program (UNM ASAP) aged 18 or older.
 - Over 70% of patients at UNM ASAP on medication assisted treatment use methadone
- B. Subjects who sign a consent form.

Exclusion Criteria

- A. Subjects who are allergic to naloxone and its inactive ingredients.
 - Inactive ingredients: buffering agents
- B. Subject younger than 18.

5. Number of Subjects

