The University of New Mexico Addiction and Substance Abuse Program (UNM ASAP) will be the research site, to include all subjects with a DSM-V diagnosis of substance use disorder. The UNM ASAP treats approximately 600 patients for substance use disorders with diagnosis of opioid dependence disorder annually. Ninety percent of these patients are treated daily as a part of their federally funded methadone maintenance treatment program. The remainder are treated with buprenorphine or naltrexone as opioid replacement therapy. Naltrexone has an FDA indication to treat opioid dependence.

We will explain the study to all potential candidates; however, 20-30% of the patients may decline to participate in the study.

We are enrolling study subjects at a current rate of approximately 6-10 subjects per month and anticipate this continuing throughout the year. Additionally, we can anticipate that our current study population is reporting a steady overdose reversal rate of 23% for every 100 patients enrolled. This number has not changed since July 2016.

Power analysis: the occurrence of opioid overdose death at the UNM ASAP is approximately 10% annually. With a sample size of 500 people we will have 80% power to detect a 20% difference in mortality at alpha level of 0.05.

6. Study Timelines

The research team submitted the initial IRB application at the beginning of October 2015. Recruitment at UNM ASAP will start in January 2016, after receiving IRB approval. The research team will follow the study subjects for one year and will close the study when qualitative interviews have been completed.

If the IIS is approved, the research team will begin the logistic regression analysis as soon as possible. Once the IRB approves the qualitative modifications, the face-to-face 1:1 interviews will begin with the study subjects.

The recruitment for the Second Year Study will begin June 1, 2017 at UNM ASAP, after receiving IRB approval for protocol amendment. The research team will follow a study subject for one year and will close the study when qualitative interviews have been completed.

7. Study Endpoints

There are four endpoints in this study:

- 1. Number of fatal over dose deaths and near fatal overdoses averted by use of naloxone auto-injector co-prescribing from the University of New Mexico Addiction and Substance Abuse Program (UNM ASAP)

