Investigators at UNM ASAP will distribute naloxone rescue kits to all study subjects. Naloxone is a prescription medication administered intravenously, subcutaneously or intramuscularly. In this study, the research team will use the naloxone auto-injector which is the only product FDA approved and labeled for use by family members or caregivers for emergency therapy wherever opioids are present. The research team will distribute the kits at the initial visit and provide education on drug overdose and rescue method from an overdose (education materials: see Appendix 2: A Patient's Guide to Evzio and Appendix 9: Opioid Overdose Toolkit) upon receiving informed consent. The education material covers education on opioid overdose and how to use the auto-injector. Education will be provided not only for patients but also, if the patient agrees, their bystander (bystander is defined as a caregiver, such as family member, friend, etc.) at initial visit and follow-up visits. According to the New Mexico Good Samaritan Law, any bystanders of patient are able to provide naloxone when drug overdose occurs. Thus, we will educate patients and their bystanders on the signs and symptoms of drug overdose due to opioids, drug overdose deaths and its risks (Appendix 9), how to use naloxone auto-injector (Appendix 2). If the patient would like to be enrolled in the study without a bystander present, he/she will be educated on the use of intramuscular naloxone and asked that they educate their friends and/or family. The subjects will return to UNM ASAP every three months after the initial visit for a follow-up. The following figure describes the procedures the investigator will carry out during each visit.

Initial Visit: Assess inclusion/exclusion criteria, obtain consent, results of urine drug screening test, and baseline information, provide face to face opioid education (individual or group education – up to 6 people in a group) and how to use naloxone auto-injector, and distribute one naloxone auto-injector carton prior to the next study visit (there are 2

14 | [Type text]

naloxone auto-injector per carton).

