Follow-up Visit (every three months): Obtain results of urine drug screening test, monitor frequency of naloxone auto-injector use, reason for naloxone auto-injector use, provide face to face education, as needed and refill naloxone auto-injector kit as needed. When patients report opioid overdose at these follow-up visits, we will obtain further information on the overdose via patient interview. The information will include date, time, and dose of naloxone use, clinical outcome [i.e., successful opioid reversal, death, and utilization of healthcare institution (e.g., EMS, emergency room, hospitalization)], to whom the kits were used, causality [i.e., type(s) of opioid], and call 911 after utilization of the kit. We will confirm the record by accessing PowerChart, only if patients used UNM Hospital for treatment.

Month 12 (1 Year): End of study visit: Obtain results of urine drug screening test, continue to ask same questions as in Follow-up visit.

If a patient uses the naloxone prior to the scheduled clinic visit, the study team will distribute one naloxone auto-injector carton prior to the next study visit. The study team will inquire about the circumstances for the use of the naloxone auto-injector.

Optional qualitative sub-study: If a study subject is selected as a potential candidate for the qualitative study, they may be contacted by phone or in person during one of their clinic visits and have the optional sub-study consent explained to them. If the person agrees to be interviewed, this will be done at a private consult room at ASAP. This visit may take 30-45 min at the end of which they will receive a \$20 gift card.

13.Data Analysis

Statistical Analysis

Statistical analysis will be performed using STATA (College Station Texas) and SAS version 9.3 (Cary, NC, United States).

The research team will collect the data and will use a descriptive analysis for demographic, social status, medical history, physical examinations, including vital signs (normal vs. abnormal findings), number of concomitant medications, scores of RIOSORD, and outcome related parameters listed in Section 12.

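### Section 3.1 dates the 0.4 mg study to April 30, 2017, Sections 6 and 12 follow each subject for 12 months, and no passage says which window defines the Year 1 events

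*Combined protocol and SAP*

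**What the plan says.** - Section 3.1 says that the previous ASAP study was a prospective observational study of the naloxone "0.4 mg auto-injector which took place April 4th, 2016 through April 30th, 2017".
- Section 6, on the first cohort: "The research team will follow the study subjects for one year and will close the study when qualitative interviews have been completed". It gives the Second Year Study, with recruitment from June 1, 2017, the same one-year rule.
- Section 12 counts visits from each subject's own entry: "The subjects will return to UNM ASAP every three months after the initial visit for a follow-up". The last is "Month 12 (1 Year): End of study visit".
- Section 1 (Note) and Section 7 (endpoint 4): "Between April 4th 2016 and April 4th 2017, 383 study subjects were enrolled and there were 93 reported overdose reversals". Enrolment was then running at 6-10 a month.
- Section 2, under the Year 1 heading, has undated interim counts: "Since April 2016, we have enrolled 358 patients at ASAP" and "We have documented 82 overdose reversals thus far", described as about 23 reversals per 100 enrolled. Section 5 says that this figure has not changed since July 2016.

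Section 13 gives no data cut-off, person-time measure or adjustment for length of follow-up.

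**The concern.** Read literally, these statements cannot all hold. A study that recruits until at least April 4, 2017 and ends on April 30, 2017 cannot give each subject 12 months.

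Three endpoints depend on the window:

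- **Endpoint 1** is a number of events averted, so the window sets its value.
- **Endpoint 2** contrasts subjects who performed a reversal with those who did not. Someone observed for 26 days has had far less chance to become a reverser than someone observed for a year. If collection stopped on a calendar date, date of entry is mixed into the outcome.
- **Endpoint 4** sets 2 mg against 0.4 mg. With an April 30, 2017 stop, every 0.4 mg event precedes the June 1, 2017 start of 2 mg recruitment. With a Month 12 stop, Year 1 follow-up runs to April 2018 and overlaps the 2 mg year.

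**Working it through.** **Inputs.** Start April 4, 2016 (Section 3.1). Counted from there, April 4, 2017 is day 365 and April 30, 2017 is day 391. N = 383 by day 365 (Sections 1 and 7). Planned follow-up is 365 days each (Sections 6 and 12). The late enrolment rate is 6-10 a month (Sections 1, 5 and 7).

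**The plan's own figure.** 82/358 = 22.9 per 100 enrolled, which reproduces the stated 23. The later counts give 93/383 = 24.3 per 100. Both are per subject enrolled; the documents give no person-time.

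**Individual subjects.** For entry on day t, follow-up by April 30, 2017 is min(365, 391 - t), and the part of the planned year falling after that date is max(0, t - 26).
- A full 12 months needs t ≤ 26, that is, entry by April 30, 2016.
- Entry on day 365 leaves 391 - 365 = 26 days.

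**The cohort.** Averaging max(0, t - 26)/365 needs an enrolment curve, which is not given. For even entry over days 0 to 365 the average is 339²/(2 × 365) = 157.4 days, and 157.4/365 = 43.1%. Observed person-years are then 383 × (1 - 0.431) = 218. Other assumed curves:

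| Assumed Year 1 enrolment | Share of planned follow-up after April 30, 2017 | Person-years by that date (of 383) |
|---|---|---|
| Most in the first 3 months, then 6-10 a month | 13-18% | 332-314 |
| Exponential decline ending at 6-10 a month | 23-28% | 294-277 |
| Linear decline to zero | 27% | 281 |
| 358 evenly, then the last 25 at 6-10 a month | 29-36% | 271-245 |
| Even to April 4, 2017 | 43% | 218 |
| Even to April 30, 2017 | 47% | 204 |

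Even enrolment means 383/12 = about 32 a month, which does not fit the stated 6-10. It is an upper case.

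**Can later events be projected?** One could carry forward a constant rate per person-year. With even enrolment, person-time to April 4, 2017 is 383/2 = 191.5 years, so the rate is 93/191.5 = 0.486 a year, and 0.486 × (383 - 218) = about 80 reversals after April 30, 2017. The other curves give fewer, down to about 15-22 with very early enrolment.

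The constant rate fails against the protocol's own report. By July 31, 2016 (day 118), evenly enrolled subjects had been in the study 59 days on average, so the model predicts 0.486 × 59/365 = 7.9 per 100 enrolled. The other curves predict about 6-7. Section 5 reports 23 per 100, unchanged since July 2016. If 23 per 100 is instead a plateau, 383 subjects yield 0.23 × 383 = 88, and 93 were already reported, so later events could be few. The documents do not decide between these.

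**The case against.** The strongest reply is that Section 3.1 is a past-tense description of a previous study, not a stopping rule. The date may bound enrolment or dispensing. The operative follow-up text is consistent: one year in Section 6, stated for both cohorts, and Month 12 in Section 12. On that reading nothing is lost and one sentence is unclear. This stands as a possible reading. But no passage calls April 30, 2017 an enrolment close, and none gives a data cut-off, so either reading needs an edit.

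Several stronger inferences should not be drawn:

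- **That a known share of follow-up, or dozens of reversals, was lost.** The shares rest on assumed curves, and the constant-rate event counts conflict with Section 5.
- **That the 12-month rule guarantees a concurrent 0.4 mg group.** Section 12 refills kits as needed, and the documents do not say which strength Year 1 subjects received after June 1, 2017.
- **That shorter follow-up biases endpoint 4.** Doses needed per reversal is a per-event measure. Fewer events cost precision, but truncation does not by itself distort it.
- **That the plan compares a partly followed Year 1 with a fully followed Year 2 on reversal counts.** Section 13 specifies no such comparison.

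It is also fair that Version 5.0 is dated 9/11/2018, after anyone enrolled by April 4, 2017 would have passed Month 12. What was collected is by then largely a fact to report. That makes the clarification easier, not unnecessary.

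**Conclusion.** The inconsistency is real and should be resolved. The text supports two Year 1 windows, and they give different event sets for endpoints 1 and 4 and different reverser status for endpoint 2. That conclusion needs only the dates and visit schedule in the protocol.

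Its size is conditional. If April 30, 2017 closed enrolment or dispensing, no follow-up is lost. If it ended data collection, the share of planned Year 1 follow-up excluded is roughly 13-18%, 23-36% or 43-47% for very early, declining or even enrolment, assuming no dropout. The declining range is the more compatible with 6-10 a month late in the year; the even range is an upper case. No reliable number of affected reversals can be given.

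**What to change.** Reconcile Section 3.1 with Sections 6 and 12, and state one Year 1 data window in Section 3.1 and Section 13.

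- If April 30, 2017 closed enrolment, say so in Section 3.1 and count Year 1 events to each subject's Month 12 visit.
- If data collection stopped then, correct Sections 6 and 12 for Year 1.

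In either case:

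- Report reversals per person-time beside the crude count.
- Account for each subject's follow-up time in the endpoint 2 logistic regression.
- Classify each endpoint 4 event by the strength actually used and its date, and show any 0.4 mg events from June 1, 2017 on separately.

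The cost is a few sentences, a re-run of the Year 1 counts and possibly a later Year 1 data lock. No visits are added, because the three-monthly and Month 12 visits are already in Section 12.

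### Endpoint 4 compares 2 mg with 0.4 mg, but the only 0.4 mg data described come from the earlier Year 1 study, so strength is nearly aligned with calendar period and no adjustment is planned

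*Combined protocol and SAP*

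**What the plan says.** Section 3.3 and Endpoint 4 (Section 7) set the aim: "Study the 2 mg Evzio autoinjector product to prospectively analyze the difference in doses (2 mg vs. 0.4 mg) needed to reverse an overdose". The 2 mg goal is 100 patients in one year and 20 to 30 reversals. Endpoint 4 places the Year 1 totals, 383 subjects and 93 reversals, beside that goal.

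Section 3.1 describes the 0.4 mg work as a "prospective observational study using the naloxone 0.4 mg auto-injector which took place April 4th, 2016 through April 30th, 2017". Section 3.3 lists the 2 mg product among the new studies, and Section 6 adds: "The recruitment for the Second Year Study will begin June 1, 2017 at UNM ASAP". The Year 1 account in Section 2 calls that study nonrandomized: "we have enrolled 358 patients at ASAP in our prospective nonrandomized clinical trial using the Evzio autoinjector". The available text describes no concurrent 0.4 mg group and no rule for who receives which strength.

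On follow-up, Section 6 says: "The research team will follow the study subjects for one year". At follow-up visits Section 12 tells staff to "provide face to face education, as needed and refill naloxone auto-injector kit as needed", without naming a strength. Section 33 lists both.

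Section 13 plans chi-square or Fisher tests and t or Wilcoxon tests. It does not name strength as a factor, and it plans no adjustment for period or for the opioid involved.

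**The concern.** The objective calls the contrast prospective. Each year's data may well be collected prospectively, but the comparison of strengths sets a new cohort against an earlier one. Anything that changed between the two years is then mixed with strength.

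The protocol supplies a mechanism. Its background section on treating overdose (Section 2c) says that naloxone dosing depends on the quantity of opioid taken, its affinity for the receptor, the patient's weight and how far the opioid penetrates the central nervous system. Nothing in the design holds these constant from one year to the next. If the opioids behind community overdoses changed, the number of doses per reversal could change with no effect of strength. A change in the other direction could hide a real effect.

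A better test or a larger sample would not cure this. An unadjusted Year 1 against Year 2 comparison estimates strength and period together.

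**Working it through.** **1. The plan's own figure.** The only planning number for Endpoint 4 is 20 to 30 reversals from 100 patients. The Year 1 rates are 82/358 = 22.9 per 100 (Section 2) and 93/383 = 24.3 per 100 (Section 7). So 100 patients give about 23 to 24 reversals, and the figure reproduces. No effect size, variance or power is stated for 2 mg against 0.4 mg, so there is nothing further to reproduce.

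**2. Dates side by side.**
- 0.4 mg: April 4, 2016 to April 30, 2017 (Section 3.1).
- Second-year recruitment: from June 1, 2017 (Section 6). That this is the 2 mg work follows from Section 3.3.
- By enrolment, the two strengths do not overlap. By date of overdose they may: a subject enrolled late in Year 1 and followed for a full year would still be in follow-up after June 1, 2017.

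**3. What a period shift would do (illustration).** The documents give no distribution of doses per reversal. Assumptions: 30% of Year 1 reversals need a second device; strength has no effect; reversals are independent; 93 reversals in Year 1 against 23 in Year 2; Fisher's exact test, two-sided 0.05. The rejection probability is the sum, over all pairs (x, y) with Fisher p < 0.05, of Bin(x; 93, 0.30) × Bin(y; 23, 0.30 + shift).

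| Period shift | 20 reversals with 2 mg | 23 | 30 |
|---|---|---|---|
| 0 points | 3.4% | 3.8% | 3.9% |
| +10 points | 12.1% | 13.5% | 15.0% |
| +20 points | 36.4% | 39.5% | 46.7% |

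A milder assumption gives less: 18% against 24% rejects in 9.3% of studies, and 18% against 30% in 22.7% (93 against 23 reversals).

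**4. Could same-period 0.4 mg events be the comparator?** Suppose the 100 subjects given 2 mg enrol evenly over the 365 days from June 1, 2017, which is day 423 counted from April 4, 2016. If Year 1 enrolment took E days with one year of follow-up each, the overlap lasts L = E + 365 − 423 days. The 2 mg person-years inside it are 100 × (L/365)²/2.

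- E = 183: L = 125, person-years = 100 × (125/365)²/2 = 5.9.
- E = 365: L = 307, person-years = 100 × (307/365)²/2 = 35.4.

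If the 20 to 30 reversals accrue over the full 100 person-years, the rate is 0.2 to 0.3 per person-year. If they accrue in the first calendar year (50 person-years), it is 0.4 to 0.6.

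- E = 183: 5.9 × 0.2 = 1.2 up to 5.9 × 0.6 = 3.5 reversals with 2 mg.
- E = 365: 35.4 × 0.2 = 7.1 up to 35.4 × 0.6 = 21.2.

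The overlap may therefore hold anywhere from about 1 to 21 reversals with 2 mg.

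**The case against.** The strongest reply is that this is a pilot which openly calls its earlier work nonrandomized and observational. Endpoint 4 is the last of four and carries no power claim. Section 12 already records the date, time and dose of each naloxone use, the type of opioid and the outcome. Section 16 records other substances used, and Section 33 requires dispensing logs. All of this stands. It lowers the severity and makes the repair cheap, but recording these variables does not amount to planning to use them, and Section 13 does not.

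A reader might infer several stronger things that the documents do not support:

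- **That the plan names Year 1 as the comparator.** No sentence does. It is the only 0.4 mg source described, and part of the text between Sections 9 and 12 was not available to check.
- **That strength and period are wholly inseparable.** Some 0.4 mg kits may have been used after June 1, 2017, and the refill text leaves open whether Year 1 subjects could hold 2 mg kits.
- **That the plan claims a causal effect of strength.** It states no such conclusion. The risk lies in how the wording of the objective would be read.
- **That differences between the enrolled cohorts are the main bias.** Section 2 reports that 81 of 82 reversals were in community members, so the list of enrollees says little about who overdosed.
- **That a same-period comparison solves the problem.** It may contain very few events. It would also set Year 1 subjects late in follow-up against new enrollees.

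Nor do the documents show that the opioids involved changed between the years. Section 2c supports the mechanism, not its occurrence.

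**Conclusion.** The concern holds as a limit on what Endpoint 4 can conclude. Strength is nearly, not provably totally, aligned with calendar period, and the planned analysis does nothing to separate them.

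The size and direction of any bias are unknown. The illustration shows that it could matter: with the assumed 30% baseline, no strength effect and 93 against 23 reversals, a shift of 10 to 20 points raises the rejection rate from 3.8% to about 14% to 40%. Those shifts and the baseline are assumptions, and milder ones give smaller figures.

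This should be fixed. It does not invalidate the pilot or its other endpoints.

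**What to change.** Amend Section 3.3, Endpoint 4 and Section 13:

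1. Make the reversal event the unit of analysis. Classify it by the strength actually injected, taken from the event interview and the dispensing log, not by enrolment year. Report mixed-strength events separately.
2. Stratify or adjust the comparison for opioid type and co-used substances, which are already recorded. Keep the model small, because only 20 to 30 reversals with 2 mg are planned.
3. Describe the contrast as a comparison with a largely historical 0.4 mg cohort, and state that residual period effects prevent a causal claim about strength.
4. Reconcile Section 3.1 with Section 6 on how long Year 1 subjects were followed, and the Section 12 refill text with the two strengths in Section 33. If 0.4 mg events after June 1, 2017 exist, report the same-period comparison as exploratory only.

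The cost is protocol wording and a modest amount of analysis on data already collected; no new subjects or visits are needed. The estimate will be slightly less precise and the stated conclusion weaker.

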Although drug overdose death rates varied by county in New Mexico, figures from the New Mexico Department of Health (NMDOH) show that the age-adjusted drug overdose death rate in New Mexico was 24.1 per 100,000, and illicit drug use and prescription drug use were equally contributed to the deaths.^{7,9} Bernalillo County, where the University of New Mexico Hospital study site is located, has the highest population in New Mexico (estimated 662,564 in April 2010), and approximately 30% of New Mexico's residents live in Bernalillo County.¹⁰ Bernalillo County experienced the 10th highest drug overdose death rate (25.4 per 100,000) in New Mexico between 2008 and 2012.⁷ This is greater than the U.S. average and the rate of New Mexico. Therefore, prevention of drug overdose deaths is a socially and epidemiologically critical issue in Bernalillo County, and any interventions for the prevention of drug overdose deaths must be established immediately.

c. Use of naloxone in the field to treat opioid overdose

• Treatment of Drug Overdose

The increase in deaths due to opioid overdose has contributed to the development of community-based overdose prevention programs, such as Project Lazarus, overdose education and naloxone distribution (OEND), and Project DAWN.¹¹⁻¹³ Naloxone is considered the primary antidote for opioid overdose and is vital in preventing fatal events. It is a competitive *mu* opioid-receptor antagonist that reverses opioid intoxication and is given via a parenteral, intranasal, or pulmonary route.¹⁴ Naloxone's onset of action is seen in less than two minutes and lasts 20 to 90 minutes.¹⁴ Dosing of naloxone is empirical, depending on many factors, including the quantity of opioid ingested, relative

affinity for the *mu* opioid-receptor, patient weight, and degree of penetration of the opioid into the central nervous system.¹⁴ Initially, a 0.04 mg dose of naloxone should be given intravenously for respiratory depression and other symptoms associated with opioid overdose.¹⁴ If the patient does not respond, the dose should be increased every two minutes to a maximum of 15 mg.¹⁴ For intramuscular or subcutaneous administration, a single dose of 0.4 mg is given, and it may repeat every 2 to 3 minutes until emergency medical assistance becomes available.¹⁴

• Project Lazarus¹¹

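### The 10% annual overdose-death rate behind the power statement is unsourced and hard to reconcile with the protocol's own figures, and the stated 80% power does not follow even if 10% is accepted

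*Combined protocol and SAP*

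**What the plan says.** Section 5 (Number of Subjects) gives the whole power analysis in two sentences. The first sets the baseline: "the occurrence of opioid overdose death at the UNM ASAP is approximately 10% annually". The second draws the conclusion: "With a sample size of 500 people we will have 80% power to detect a 20% difference in mortality at alpha level of 0.05". The section does not give a source for the 10%, the comparator, the allocation, the sidedness, the test, or whether the 20% is relative or absolute. It puts the clinic population at about 600 patients a year.

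Other sections bear on the same figure:

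- Section 2(b) says of the county where the site lies that it "has the highest population in New Mexico (estimated 662,564 in April 2010"), about 30% of the state's residents, and that "Bernalillo County experienced the 10th highest drug overdose death rate (25.4 per 100,000") for 2008–2012. It gives an age-adjusted state rate of 24.1 per 100,000.
- The Year-1 summary in Section 2 describes a "prospective nonrandomized clinical trial using the Evzio autoinjector" with 358 patients enrolled and 82 reversals, and adds: "Only one of the reported overdose reversals was from the study patients at ASAP". Section 1 gives 383 subjects and 93 reversals for the full first year. Neither place gives a number of deaths among enrolled subjects.
- On follow-up, Section 6 says: "The research team will follow the study subjects for one year".

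**The concern.** The baseline death rate is the only mortality input to the power statement, and fatal overdose is part of the first objective and the first endpoint. A rate of one death per ten patients per year would be striking for a single outpatient program, and it can be checked against numbers that the protocol itself supplies. The figure might be a rate of all overdoses that has been labelled a death rate.

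Two things are at stake. A reader of Section 5 will believe that the study can show an effect on mortality when it may have almost no ability to do so. And 10% is the only clinic-level mortality benchmark in the document. In a study with no concurrent control described, a low observed death rate could later be set beside it and read as an effect of the kits.

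**Working it through.** **Step 1. Reproduce the stated 80%, accepting 10%.** The inputs from Section 5 are a baseline of 0.10, 500 people, alpha 0.05 and a 20% difference. Comparator and sidedness are not given, so I tried the plausible readings. A 20% relative reduction is 0.10 versus 0.08.

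*Two groups of 250 (assumed split), two-sided, pooled normal approximation:*

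power = Φ{[|p1 − p2|√n − 1.96√(2p̄q̄)] / √(p1q1 + p2q2)}

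= Φ{[0.02 × 15.81 − 1.96 × √0.1638] / √0.1636} = Φ{(0.316 − 0.793)/0.404} = Φ(−1.18) = **11.9%**

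*500 people against a fixed 10%, two-sided:*

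power = Φ{[|p1 − p0|√n − 1.96√(p0q0)] / √(p1q1)}

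= Φ{[0.02 × 22.36 − 1.96 × 0.30] / √0.0736} = Φ{(0.447 − 0.588)/0.271} = Φ(−0.52) = **30.2%** (exact binomial 28.7%)

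Other readings at 10%:

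- One-sided: 19.4% (250 versus 250) or 43.2% (500 against a fixed rate).
- 500 per group: 19.6% two-sided, 29.5% one-sided.
- Absolute difference: a 20-point fall from 10% is impossible. A 20-point rise (10% versus 30%, 250 per group) gives more than 99.9%.

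No reading gives 80%. Two-sided 80% power for 0.10 versus 0.08 needs 3,213 per group, or 1,666 in a one-sample test. Conversely, 500 people would reach 80% for a 20% relative reduction only at a baseline of about 27% (one sample) or 62% (250 per group).

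**Step 2. Check 10% against the county and state figures.**

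- Clinic deaths implied: 0.10 × 600 = 60 a year.
- County deaths implied: 25.4/100,000 × 662,564 = 168 a year. Share: 60/168 = 36%.
- State population implied: 662,564/0.30 ≈ 2.21 million. Deaths: 2.21 million × 24.1/100,000 ≈ 532. Share: 60/532 = 11%.
- Ratio of rates: 10,000 per 100,000 against 25.4 per 100,000, about 394-fold.

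The 60 are opioid deaths, while the 168 and 532 count all drugs, so this comparison favours the 10%.

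**Step 3. Check 10% against Year 1.** A full year for each subject would imply 0.10 × 358 = 36 to 0.10 × 383 = 38 deaths. If entry was uniform over the year (an assumption), exposure is about half and the figure is 18–19. The documents give no death count to set beside these numbers.

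**Step 4. Power if the true rate is lower.** The documents give no replacement rate, so 1–5% is an assumption. It still allows for a risk 39 to 197 times the county rate (1,000/25.4 and 5,000/25.4). The figures are for a 20% relative reduction, two-sided, by the formulas of Step 1:

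| Assumed annual rate | Expected deaths in 500, no effect | Power, 250 vs 250 | Power, 500 vs fixed rate |
|---|---|---|---|
| 10% (as stated) | 50 | 11.9% | 30.2% |
| 5% | 25 | 7.8% | 15.0% |
| 2% | 10 | 5.2% | 7.0% |
| 1% | 5 | 4.2% | 4.6% |

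These are chances of rejecting in the direction of a reduction. With as few as 5–10 expected deaths the normal approximation is rough, but the conclusion does not depend on its precision.

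**The case against.** The best defence is that nothing in the protocol directly contradicts 10%. The county and state rates describe the general population and all drugs, the state rate is age-adjusted, and the state population is back-calculated from an approximate 30%. Patients in treatment for opioid dependence should far exceed those rates, and some may live outside the county. This stands as a caution on wording: the figures are very hard to reconcile, but they are not a strict contradiction. It does not remove the difficulty, because residence elsewhere in the state still leaves one clinic supplying about 11% of all overdose deaths in the state.

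A reader might infer from the Year-1 summary that almost no subjects died and that 10% is thereby refuted. The documents do not support that. The summary counts reversals and is silent on deaths. Outcomes are self-reported at visits (Sections 12 and 16), so a subject who died could not report. Entry was staggered, and subjects already held kits. Year 1 neither confirms nor refutes the rate.

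A reader might also infer that the inflated baseline is what makes the 80% wrong. It is not the main cause: most of the shortfall is present at 10% itself. Nor does a lower baseline reduce power on every reading. For a fixed absolute rise of 2 points with 250 per group, power goes up from 10.6% at a 10% baseline to 35.8% at 1%. Since the objective is to decrease deaths, the relative reduction is the relevant reading, and there power does fall.

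Finally, Section 13 names no mortality test and no comparison with a historical 10%. The current recruitment goal is 100 patients with 20–30 reversals, so correcting the rate changes no planned test and no current target. That is fair, and it limits the consequence to what Section 5 claims and how it might later be used.

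**Conclusion.** The point holds in two parts. First, the 10% death rate has no source and cannot readily be reconciled with Section 2: it implies about 60 deaths a year, roughly 36% of the county's implied total and 11% of the state's. Secondly, the 80% power is not reproducible at 10%. It is about 12% for 250 versus 250 and about 30% for 500 against a fixed rate (two-sided, 20% relative reduction), and no higher than about 43% on the one-sided one-sample reading. If the true rate is 1–5%, which is assumed, these become about 4–8% and 5–15%.

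The conclusion rests on reading the 20% as a relative reduction, the only reading consistent with an aim of fewer deaths, and on assumed comparators, because the protocol states none. It does not establish what the true rate is. One could go further and say that the study will claim a benefit by testing against 10%, but no section plans such a test. The risk is one that a single sentence can close off. This should be corrected, but it does not undermine the descriptive, regression or qualitative aims.

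**What to change.** In Section 5:

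1. Say whether 10% refers to overdose deaths or to all overdoses, and give its source, numerator and person-time.
2. If it cannot be sourced, replace it with a clinic overdose-death count over person-years from before kits were distributed, if one is available. The Year-1 rate should not be used as the baseline, because it was observed with kits in hand.
3. Restate the power with the comparator, effect scale, sidedness and test defined. Otherwise drop the power sentence and describe mortality as descriptive only.
4. State that the unsourced 10% will not be used as a historical comparator for mortality.

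The text change is a few sentences. Obtaining a pre-kit count may take more work, since the protocol describes no source of death ascertainment and limits chart confirmation to patients treated at the university hospital. If no count can be had, dropping the power sentence costs nothing beyond the edit. The downside is that the stated power becomes much less favourable or disappears.
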